### **6.13.6. Quick Inventory of Depressive Symptomatology–Self Report 16 Items (QIDS-SR16)**

The QIDS-SR16 is a self-administered 16-item instrument intended to assess the existence and severity of symptoms of depression as listed in the American Psychiatric Association’s (APA’s) *Diagnostic and Statistical Manual of Mental Disorders, 4th Edition (DSM-IV)* (APA 1994). The QIDS-SR16 scale is used to assess the potential impact of treatment on new onset or changes in depression, thoughts of death, and/or suicidal ideation severity. A patient is asked to consider each statement as it relates to the way they have felt for the past 7 days. There is a 4-point scale for each item ranging from 0 to 3. The 16 items corresponding to 9 depression domains are summed to give a single score ranging from 0 to 27, with higher scores denoting greater symptom severity. Additional information and the QIDS-SR16 questions may be found at the University of Pittsburgh IDS/QIDS resource page (WWW).

The 9 domains assessed by the instrument are defined as:

- 1) **Sleep disturbance** (initial, middle, and late insomnia or hypersomnia): the highest score recorded for the 4 sleep items: #1 (falling asleep), #2 (sleep during the night), #3 (waking up too early) and #4 (sleeping too much). Domain is missing if all items are missing.
- 2) **Sad mood**: Item #5 (feeling sad). Domain is missing if the item is missing.
- 3) **Decrease/increase in appetite/weight**: the highest score recorded for the appetite/weight items: #6 (decreased appetite), #7 (increased appetite), #8 (decreased weight within the last 2 weeks), and #9 (increased weight within the last 2 weeks). Domain is missing if all items are missing or not applicable.
- 4) **Concentration**: Item #10 (concentration / decision making). Domain is missing if the item is missing.
- 5) **Self-criticism**: Item #11 (view of myself). Domain is missing if the item is missing.

- 6) **Suicidal ideation:** Item #12 (thoughts of death or suicide). Domain is missing if the item is missing.
- 7) **Interest:** Item #13 (general interest). Domain is missing if the item is missing.
- 8) **Energy/fatigue:** Item #14 (energy level). Domain is missing if the item is missing.
- 9) **Psychomotor agitation/retardation:** the highest score recorded for the 2 psychomotor items: #15 (feeling slowed down) and #16 (feeling restless). Domain is missing if all items are missing.

The QIDS-SR16 total score is the sum of the above domain scores. The total score will be missing if any domain score is missing.

The QIDS-SR16 total scores are categorized as follows:

- None (no depression): 0 – 5
- Mild: 6 – 10
- Moderate: 11 – 15
- Severe: 16 – 20
- Very severe: 21 – 27.

The following summaries will be produced for QIDS-SR16 total score category by treatment groups for the Safety Population during the Period 2:

- The number and percentage of patients falling into each QIDS-SR16 total score category at each scheduled visit.
- Shift from maximum baseline to each postbaseline visit in QIDS-SR16 total score category.
- The number and percentage of patients falling into the following categories based upon the maximum postbaseline QIDS-SR16 total score:
  - Improved; maximum postbaseline category < maximum baseline category.
  - Worsened; maximum postbaseline category > maximum baseline category.
  - Same; maximum postbaseline category = maximum baseline category.

In addition, the number and percentage of patients falling into the following groups based upon the maximum postbaseline QIDS-SR16 item 12 (Thoughts of Death or Suicide) score will be summarized by treatment groups for Safety Population during Period 2:

- Improved; maximum postbaseline QIDS-SR16 item 12 score < maximum baseline item 12 score.
- Worsened; maximum postbaseline QIDS-SR16 item 12 score > maximum baseline item 12 score.
- Same; maximum postbaseline QIDS-SR16 item 12 score = maximum baseline item 12 score.

### 6.13.7. Columbia-Suicide Severity Rating Scale (C-SSRS)

The C-SSRS is an assessment tool that evaluates suicidal ideation and behavior. Information on the C-SSRS scale can be found through the C-SSRS resource page (Columbia resources page [WWW]).

Specifically, the following outcomes are C-SSRS categories and have binary responses (yes/no). The categories have been re-ordered from the actual scale to facilitate the definitions of the composite and comparative endpoints, and to enable clarity in the presentation of the results.

Category 1 – Wish to be Dead

Category 2 – Non-specific Active Suicidal Thoughts

Category 3 – Active Suicidal Ideation with Any Methods (Not Plan) without Intent to Act

Category 4 – Active Suicidal Ideation with Some Intent to Act, without Specific Plan

Category 5 – Active Suicidal Ideation with Specific Plan and Intent

Category 6 – Preparatory Acts or Behavior

Category 7 – Aborted Attempt

Category 8 – Interrupted Attempt

Category 9 – Actual Attempt (non-fatal)

Category 10 – Completed Suicide.

Self-injurious behavior without suicidal intent is also a C-SSRS outcome (although not suicide-related) and has a binary response (yes/no).

Composite endpoints based on the above categories are defined below.

- **Suicidal ideation:** A “yes” answer at any time during treatment to any 1 of the 5 suicidal ideation questions (Categories 1-5) on the C-SSRS.
- **Suicidal behavior:** A “yes” answer at any time during treatment to any 1 of the 5 suicidal behavior questions (Categories 6-10) on the C-SSRS.
- **Suicidal ideation or behavior:** A “yes” answer at any time during treatment to any 1 of the ten suicidal ideation and behavior questions (Categories 1-10) on the C-SSRS.

Given that few or no suicidal ideation or behaviors are anticipated, C-SSRS will be listed by patient and visit. Only patients that show suicidal ideation/behavior or self-injurious behavior without suicidal intent will be displayed (that is, if a patient’s answers are all ‘no’ for the C-SSRS, then that patient will not be displayed). However, if a patient reported any suicidal ideation/behavior or self-injurious behavior without suicidal intent at any time point, then all their ideation and behavior will be displayed, even if not positive. Note, missing data should not be imputed.

The Self-Harm Supplement Form is a 1-question form that is completed, at any visit, including baseline visit, that asks for the number of suicidal behaviors, possible suicidal behaviors, or nonsuicidal self-injurious behaviors the patient has experienced since the last assessment. For each unique event identified, a questionnaire (Self-Harm Follow-up Form) which collects supplemental information on the self-injurious behavior is to be completed. The Self-Harm data

will be listed by patient and visit if number of events on Self-Harm Supplement Form is not zero in the CRF ‘*Self Harm Questionnaire Supplement.*’

### **6.13.8. Immunogenicity**

#### **6.13.8.1. Definitions and Terms**

[figure not shown]
The following sample- and patient-related definitions and parameters will be used to describe the immunogenicity data.

##### **6.13.8.1.1. Sample Category Definitions**

Samples are classified into the following categories:

- **Unevaluable sample:** Sample could not be tested for ADA due to sample loss, mishandling, or errors in collection, processing, storage, and so on.
- **Anti-drug antibody (ADA) Positive sample:** The presences of ADA is detected and confirmed. The samples are reported as positive. If the sample is positive, a titer value is reported.
- **Neutralizing anti-drug antibody (NAb) Positive sample:** NAb are reported as detected.
- **Anti-drug antibody (ADA) Negative sample:** The presence of ADA is not detected and the assay drug tolerance level is not exceeded.
- **Neutralizing anti-drug antibody (NAb) Negative sample:** The presence of NAb is not detected and the assay drug tolerance level is not exceeded.
- **Anti-drug antibody (ADA)/NAb Inconclusive sample:** when ADA/NAb is not detected in a sample but drug is present in the same sample at a level that can cause interference in the ADA/NAb detection method. The negative ADA/NAb result cannot be confirmed and the sample should be considered inconclusive.
  - Confirmation of a negative ADA result is based on ixekizumab concentrations and on the limit of drug tolerance of the NAb assay.

Figure RHBX.6.5 illustrates the relationship of some of the above terms.

Abbreviation: ADA = anti-drug antibody.

**Figure RHBX.6.5. Sample definitions.**

#### 6.13.8.1.2. Patient Category Definitions

The following categories are applied to patients based on the classification of their samples:

- **Unevaluable patient:** a) a patient with no evaluable baseline sample and/or no evaluable postbaseline samples; b) a patient with an evaluable baseline sample but no evaluable postbaseline sample; c) a patient with no evaluable baseline sample, but whose evaluable postbaseline values are all ADA positive or a mix of positive and negative. (Note: If all postbaseline samples are negative, the patient is considered 'evaluable' and will be classified as ADA-negative).
- **Evaluable patient:** a) Patient with an evaluable baseline sample and at least 1 evaluable postbaseline sample (that is, sample after administration of study drug); b) patient with no evaluable baseline sample whose evaluable postbaseline samples are all ADA negative.

Figure RHBX.6.6 illustrates the relationship of the above terms.

[figure not shown]

Figure RHBX.6.6. Patient category definitions.

**6.13.8.1.3. Definitions for Clinical Interpretation of Assay Results**

**Baseline and postbaseline**

Baseline and postbaseline definition for immunogenicity analyses are defined in [Table RHBX.6.10](#) based on the purpose of the analyses.

**Table RHBX.6.10. Baseline and Postbaseline Definition for Immunogenicity Analyses in Period 2**

[figure not shown]
Analysis Purpose	Analysis Population	Treatment Group	Baseline Definition	Postbaseline Definition
Incidence of TE-ADA during Week 0-16	Safety Population	Group 1: PBO IXE 80mg Q4W IXE 80mg Q2W Total Ixe	Last non-missing observation on, or prior to the date of the first injection of study drug at Week 0 (before drug administration)	Week 0-16
Incidence of TE-ADA during Week 0 -52 while patients on Ixekizumab exposure	All Ixekizumab Exposure Safety Population a	Group 2: IXE 80mg Q2W – Q2W b IXE 80mg Q4W – Q4W c PBO - IXE 80mg Q2W d IXE 80mg Q4W – Q2W e All IXE 80mg Q2W f	Last non-missing observation on, or prior to the date of the first injection of ixekizumab, that is, PBO – ixe 80mg Q2W, baseline is before ixekizumab 80mg Q2W rescue. For other groups, it is Week 0	Time period between the first ixekizumab injection to the last visit. For patients who may take other biologic rescues (e.g. TNFi), the postbaseline period ends prior to the start of other biologic therapy.

Abbreviations: IXE = ixekizumab; PBO = placebo; Q2W = every 2 weeks; Q4W = every 4 weeks; TE-ADA = treatment-emergent anti-drug antibody; TFFi = tumor necrosis factor inhibitor.

- a defined as all patients who received at least one dose of ixekizumab during the study.
- b includes patients with only ixekizumab 80mg Q2W exposure, regardless of whether patients were rescued by ixekzimab 80mg Q2W
- c Includes patients with only ixekizumab 80mg Q4W exposure. Patients who were rescued by ixekizuamb 80mg Q2W are not included.
- d Includes patients who were originally assigned to placebo and were later on rescued by ixekizumab 80mg Q2W.
- e Includes patients who were originally assigned to ixekizumab 80mg Q4W and were later on rescued by Ixekizumab 80mg Q2W.
- f includes groups 1 and 3.

- **baseline ADA positive (preexisting antibody):** ADA detected in a sample collected at baseline.
- **baseline ADA-negative:** ADA is not detected in a sample collected at baseline.
- **treatment-emergent anti-drug antibody (TE-ADA) positive:** a) a patient with a  $\geq 4$ -fold increase over a positive baseline antibody titer (Tier 3); or b) for a negative baseline titer, a patient with an increase from the baseline to a level of  $\geq 1:10$ .
- **treatment-emergent anti-drug antibody (TE-ADA) inconclusive patient:** A patient without a TE-ADA positive sample and with at least 1 sample for which drug levels may interfere with the ADA assay.
- **treatment-emergent anti-drug antibody (TE-ADA) negative patient:** A patient who is evaluable for TE-ADA and is not either TE-ADA positive or TE-ADA inconclusive.

Figure RHBX.6.7 illustrates the relationship of some of these terms.

Abbreviation: ADA = anti-drug antibody.

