#### **6.13.8.2.1. Analyses of Characteristics of ADA Immune Response**

The analyses of characteristics of ADA response will be conducted on all immunogenicity evaluable patients within the Safety Population for the first 16-weeks of Blinded Treatment Dosing Period 2 (Week 0 to 16), and for the All Ixekizumab Exposures Safety Population for the entire 52-week Blinded Treatment Dosing Period 2 when patients are on ixekizumab, including open label rescue with ixekizumab of 80 mg Q2W (time period when patients are on placebo will be excluded), according to [Table RHBX.6.10](#).

The overall frequency and percentage (incidence) of patients will be summarized for the TE-ADA status groups and the time-varying TE-ADA status groups. Scheduled visits, unscheduled visits, and repeat measurements will be included.

In addition, the overall frequency and percentage (incidence) of patients will be summarized for the patients who are baseline ADA positive by TE-ADA status groups. For those patients who are TE-ADA positive, a summary of titer values and the proportion of patients who are NAb positive will also be provided.

The time to the development of TE-ADA (TE-ADA positive, low titer, moderate titer, high titer, and NAb positive) will be calculated as follows:

$$\text{Time to development of TE-ADA/NAb (in weeks)} = (\text{Date of development of TE-ADA/NAb} - \text{Date of first injection of study treatment} + 1) / 7.$$

If a patient has not developed TE-ADAs/NAbs, they will be censored at the date of the last immunogenicity assessment.

Descriptive statistics, including 25th percentile, 50th percentile (median), 75th percentile, and corresponding 95% CIs as well as proportion of TE-ADA/NAb positive by endpoint summarized by treatment group, will also be provided if sufficient data is present. A Kaplan-Meier plot of the time to development of treatment-emergent ADA/NAb will be presented by treatment group, also if sufficient data is present.

For each TE-ADA status dichotomous variable (as defined in [Table RHBX.6.11](#)), summaries will be provided of the total postbaseline time in the greater-TE-ADA status for patients who were at some point postbaseline in the greater-TE-ADA status group. Postbaseline time in greater-TE-ADA status for each patient will be aggregated.

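### The 52-week antibody table has no row for the Q4W arm as randomised, or for Q4W patients while on Q4W, so its Q2W-Q2W and Q4W-Q4W rows are not like for like

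*SAP*

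**What the plan says.** Section 6.13.8.2.1 plans the antibody summaries in two parts. The first covers Weeks 0-16 in the Safety Population by assigned arm (Group 1, purpose "Incidence of TE-ADA during Week 0-16"). The second is "for the All Ixekizumab Exposures Safety Population for the entire 52-week Blinded Treatment Dosing Period 2 when patients are on ixekizumab" (Group 2).

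The footnotes to Table RHBX.6.10 define the Group 2 rows:

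- **Q2W-Q2W (footnote b):** "includes patients with only ixekizumab 80mg Q2W exposure, regardless of whether patients were rescued by ixekzimab 80mg Q2W".
- **Q4W-Q4W (footnote c):** "Includes patients with only ixekizumab 80mg Q4W exposure. Patients who were rescued by ixekizuamb 80mg Q2W are not included".
- **Q4W-Q2W (footnote e):** "Includes patients who were originally assigned to ixekizumab 80mg Q4W and were later on rescued by Ixekizumab 80mg Q2W".
- **All Q2W (footnote f):** "includes groups 1 and 3", that is, Q2W-Q2W together with placebo patients rescued to Q2W. No matching pooled Q4W row is listed.

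Baseline for the placebo-to-Q2W row is taken before rescue; "For other groups, it is Week 0". The postbaseline window is "Time period between the first ixekizumab injection to the last visit". It ends early if another biologic is started, but not at ixekizumab rescue.

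Section 6.13.8.2.1 also plans, if the data suffice, Kaplan-Meier curves by treatment group of the time from first injection to TE-ADA or NAb.

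**The concern.** Rescue is decided by the investigator, after randomisation, between Weeks 16 and 44 (Protocol 6.1). It leaves a Q2W patient in the Q2W-Q2W row, but takes a Q4W patient out of Q4W-Q4W together with the Q4W time before rescue. A reader who sets the two rows side by side to compare regimens is comparing a whole randomised arm with a subset chosen by a later event. If antibodies weaken the response, antibody-positive Q4W patients would tend to be rescued and so to leave the row.

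The Kaplan-Meier curves share the problem if they use these groups: each Q4W patient is placed on one of two curves at time zero according to whether rescue comes later.

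At stake is the 52-week TE-ADA and NAb incidence by regimen. The Week 0-16 analysis cannot supply it, because immunogenicity samples continue at Weeks 24, 28, 36 and 52 (Protocol Appendix 2).

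**Working it through.** **Row membership.** This follows from the footnotes and from Protocol 6.1, under which rescue moves Q4W patients to Q2W and leaves Q2W patients on the same regimen.

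| Patient | Group 2 row | Window |
|---|---|---|
| Q2W, never rescued | Q2W-Q2W | Week 0 to last visit |
| Q2W, rescued | Q2W-Q2W | Week 0 to last visit |
| Q4W, never rescued | Q4W-Q4W | Week 0 to last visit |
| Q4W, rescued | Q4W-Q2W | Week 0 to last visit |

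The two Q4W rows are disjoint and together hold every treated Q4W patient. Adding them gives the arm as randomised. It does not give incidence while on Q4W, because the Q4W-Q2W window is not cut at rescue: antibody that arose on Q4W before rescue is counted with antibody that arose on Q2W afterwards.

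**Size.** The documents state no TE-ADA rate, no rescue rate and no link between them, so there is no figure of the plan's to reproduce. What follows is illustration on assumed rates. The only input from the plan is about 100 patients per arm (SAP 5.2: 300 at 1:1:1).

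Let r be the fraction rescued, and let q0 and q1 be the 52-week TE-ADA incidence in never-rescued and rescued patients, all equal in the two arms, so that the regimens do not truly differ.

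- Q4W-Q4W shows q0, on 100(1 − r) patients.
- Q2W-Q2W shows (1 − r)q0 + r·q1, on 100 patients.
- Apparent gap = r(q1 − q0).

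Gap in percentage points:

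| q0 | q1/q0 | r = 20% | r = 40% | r = 60% |
|---|---|---|---|---|
| 5% | 1 | 0 | 0 | 0 |
| 5% | 2 | 1 | 2 | 3 |
| 5% | 3 | 2 | 4 | 6 |
| 10% | 1 | 0 | 0 | 0 |
| 10% | 2 | 2 | 4 | 6 |
| 10% | 3 | 4 | 8 | 12 |

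Example: q0 = 10%, q1 = 20%, r = 40%. Q4W-Q4W shows 10% on 60 patients. Q2W-Q2W shows 0.6 × 10% + 0.4 × 20% = 14% on 100. Pooling the two Q4W rows gives (60 × 0.10 + 40 × 0.20)/100 = 14%, and the gap closes. It closes in every cell of the grid.

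**The same effect from the rescue side.** With true incidence a, and rescue risk r0 in TE-ADA-negative and r1 in TE-ADA-positive patients, Q4W-Q4W shows a(1 − r1)/[a(1 − r1) + (1 − a)(1 − r0)].

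- a = 10%, r0 = 35%, r1 = 50%: 0.05/(0.05 + 0.585) = 7.9%.
- a = 10%, r0 = 35%, r1 = 65%: 0.035/(0.035 + 0.585) = 5.6%.
- a = 20%, r0 = 35%, r1 = 50% or 65%: 0.10/0.62 = 16.1%, or 0.07/0.59 = 11.9%.
- a = 10%, r0 = r1 = 40%: 10%. No bias, but 40 of 100 patients have left the row.

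A Q2W arm with the same true incidence shows a itself.

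**The case against.** The strongest defence is that the table follows one rule, the regimen actually received. Its stated purpose is incidence during ixekizumab exposure, and a patient who moved from Q4W to Q2W does not belong in a row for Q4W exposure only. That stands as a reason for keeping the existing rows. It justifies moving the time after rescue; it does not explain why the patient's Q4W time before rescue should leave every Q4W-only row.

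Three stronger readings are tempting, and the documents do not support them.

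- **Rescued Q4W patients are lost.** They are in the Q4W-Q2W row of the same table.
- **Q4W incidence is measured only in patients who did well.** Group 1 covers the whole Q4W arm for Weeks 0-16, before rescue can take effect. Q4W-Q4W can also hold patients who stopped early, and inadequate responders who only changed concomitant medication and stayed on assigned treatment (both described in SAP 6.3.1).
- **The 52-week Q4W figure will be biased low.** That needs TE-ADA-positive patients to be rescued more often, and nothing in the documents shows this.

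It is also fair to say that no planned test compares these two rows. The tested efficacy-by-TE-ADA analysis is at Week 16, the Week 52 summary is untested (SAP 6.13.8.2.2), and the adverse-event analysis puts all patients in one group (SAP 6.13.8.2.3). Section 6.13.8.2.1 does not name Group 2 for the Kaplan-Meier curves, so that part of the point is conditional.

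**Conclusion.** The point holds as a gap in the 52-week presentation. Group 2 contains neither the Q4W arm as randomised nor Q4W patients while on Q4W, and Q2W-Q2W against Q4W-Q4W is not a like-for-like comparison. Protocol 9.7.3 asks for antibody incidence by treatment group within the safety population, which Protocol 9.2.3 analyses as assigned; Group 2 gives no single row of that kind for Q4W. The protocol does allow the SAP to define further populations, so this is an omission and not a contradiction.

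The direction and size of any distortion are unknown. On the assumed grid (rescue 20-60%, never-rescued incidence 5% or 10%, rescued incidence one to three times that, no true regimen difference) the gap runs from 0 to 12 points. At zero association the only loss is patients: the row holds 80, 60 or 40 of 100. The consequence is confined to descriptive 52-week summaries and any curves drawn by these groups.

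**What to change.** In Table RHBX.6.10, Group 2:

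1. Add a pooled row of all treated patients randomised to Q4W (footnotes c and e combined), from first injection to last visit, as the 52-week counterpart of Q2W-Q2W.
2. Add as-randomised Q4W and Q2W rows, both cut at the first rescue injection. Use them for incidence on the assigned regimen and for the Kaplan-Meier curves.
3. Keep the existing rows as descriptive, and state that Q2W-Q2W and Q4W-Q4W alone are not a comparison of regimens.

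The cut-at-rescue rows should not be the only 52-week figure. If antibodies lead to rescue, censoring at rescue is informative. Follow-up is also shorter: a patient rescued at Week 20 has no scheduled immunogenicity sample between Week 16 and the cut, so a simple proportion can undercount TE-ADA. Applying the same cut to Q2W drops samples from patients whose regimen did not change, which is the price of one common rule. The SAP should state these limits.

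The cost is some table wording and a few extra output columns.

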**Figure RHBX.6.7. Relationship of terms for clinical interpretation of assay results for evaluable patients.**

[figure not shown]
- **Incidence of TE-ADA:** Patients with TE-ADA as a proportion of the evaluable patient population during the treatment period. This excludes unevaluable patients.

All ADA positive samples will be evaluated for NAb. Definitions for NAb patient status will be defined as follows:

- **NAb-positive patient:** A patient where a NAb positive result is detected for  $\geq 1$  TE-ADA positive samples.
- **NAb-inconclusive patient:** A patient without a NAb positive sample and with at least 1 sample for which drug levels may interfere with the NAb assay.

- NAb-negative patient:** A patient who is evaluable for NAb and is not either NAb positive or NAb inconclusive.

A flow chart that reflects the connection between the analytical test results and the clinical interpretation based on the definitions is shown in [Figure RHBX.6.8](#).

Abbreviations: ADA = anti-drug antibody; NAb = neutralizing antibody; PK = pharmacokinetics.

